9.3.17 Subject-Level Study Treatment

This study consists of Screening, Treatment, and Follow-up periods. For a data record, the planned treatment and dose level will be based on a specific study period as follows:

Study Period	Planned Treatment
Screening	Placebo or tildacerfont (50 mg QD)
Treatment Period (Day 1 to Week 4)	Placebo or tildacerfont (50 mg QD)
Treatment Period (post-Week 4 to Week 8)	Placebo or tildacerfont (100 mg QD)
Treatment Period (post-Week 8 to Week 12)	Placebo or tildacerfont (200 mg QD)

The actual study drug treatment and dose level will be the study drug and dose level a subject was on when a data record was measured/assessed.

9.3.17.1 Record-Level Actual Treatment and Dose for an Adverse Event

TEAEs are those AEs with onset date from the date of first dose of randomized study drug until the end of the study (Follow-up). The treatment will be the randomized study treatment (tildacerfont or placebo) and the dose level (50 mg QD, 100 mg QD, 200 mg QD) will be the actual tildacerfont dose received on the onset date of the TEAE records.

Post-treatment AEs (within 30 days after study drug discontinuation) will be assigned the last treatment and dose level that the subject was on before study drug discontinuation. Post treatment AEs after 30 days post study drug discontinuation will be assigned to no treatment.

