3.1.2. Study Visits

Each subject will undergo a Screening Visit within 30 days of Day 1, three 4-week treatment periods, and a 30-day follow-up period. Subjects may also attend a DHEAS Screening Visit if needed (see [Section 3.1.2.1](#)). See the Schedule of Activities for full details of each study visit ([Section 12.2](#)).

Clinic visits should be scheduled for early in the morning to accommodate morning laboratory assessments (at 8 A.M. \pm 1 hour).

Sites will make scheduled telephone contacts to all subjects at Weeks 2, 6, and 10 to assess for the occurrence of any AEs and the initiation of new concomitant medications. The Early Termination Visit/Follow-up Visit may also be conducted by telephone at the discretion of the Investigator.

Subjects should be instructed to telephone sites if they have any concerns about their health and/or to report AEs.

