5.1. Treatment Administration

All subjects will be treated with 3 doses of oral tildacerfont (50 mg, 100 mg, or 200 mg QD), or placebo for 12 weeks.

Study drug will be taken with the subject's evening meal (see [Section 4.2.1](#)) between 6 P.M. and midnight.

Study drug will be dispensed at Day 1, Week 4, and Week 8. Only authorized study staff may dispense study drug. Sites will provide subjects with dosing instructions.

Criteria for study drug discontinuation are provided in [Section 6.1](#).

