5.5. Study Intervention Compliance

Study drug will be returned for accountability at Week 4, Week 8, and Week 12. The Investigator is responsible for ensuring that dosing is administered in compliance with the protocol.

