7.1.5. Clinical Laboratories

Clinical laboratory assessments include hematology, clinical chemistry, including cortisol, HbA1c, coagulation, lipid panel, thyroid panel, urinalysis, and a hormone panel. eGFR for screening will be calculated from blood creatinine measured as part of Screening clinical chemistry. A complete list of study-required clinical laboratory tests is provided in [Section 12.4](#).

Samples for clinical laboratories will be collected consistently at the beginning of each visit at approximately 8 A.M. See the Schedule of Activities ([Section 12.2](#)).

All study-required clinical laboratory tests must be conducted in accordance with the laboratory manual and will be performed by a central laboratory.

The Investigator must review the laboratory report, document the review, and record any clinically significant laboratory findings that occur during the study in the AE section of the eCRF. Laboratory reports must be filed with the source documents. Clinically significant laboratory findings are those that are not associated with the underlying disease, unless judged by the Investigator to be more severe than expected for the subject's condition.

All laboratory tests with values considered clinically significantly during the Treatment Period or within 30 days after the last dose of study drug should be reported as AEs and repeated at least weekly until the values return to normal or baseline or are no longer considered clinically significant by the Investigator or Medical Monitor. If such values do not return to normal/baseline within a period of time judged reasonable by the Investigator, the etiology should be identified, and the Sponsor notified.

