¹ All clinic visits and telephone contacts should be performed on the indicated study days. In cases where adherence to the foregoing schedule is not possible, the following visit windows apply: ± 1 days for clinic visits and telephone contacts.

² All subjects will return to the clinic (or, at the discretion of the Investigator, be contacted via telephone) for the ETV/Follow-up Visit.

³ Will be conducted pre-dose at Day 1

⁴ A serum pregnancy test will be performed at screening. All other pregnancy tests will be urine pregnancy tests.

⁵ Blood samples will be drawn for PK measurement at 8 A.M. (± 1 hour) on clinic visit days.

⁶ Vital signs consist of systolic and diastolic blood pressure, pulse rate, respiration rate, and body temperature. Vital signs will be measured after a 5-minute rest period. Height is measured only at Screening Visit.

⁷ A full physical examination may exclude rectal, genitourinary, and breast exams.

⁸ See [Section 7.1.6](#) for details on the administration of the C-SSRS.

⁹ Abbreviated physical examinations at Visits 2 and 3 will be conducted directed by AES.

¹⁰ Blood draws for these laboratory assessment samples will be obtained at 8 A.M. (± 1 hour). On Day 1, blood draws should be performed prior to the first dose of study drug.

¹¹ Study drug will be taken daily with an evening meal (with approximately <50% fat content), which should be eaten between 6 P.M. and midnight. Study drug may be consumed up to 30 minutes after completing the evening meal, if necessary.

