9.3.14.3 Study Drug Exposure Duration (days)

The duration (days) of study drug exposure is derived from the first dose date and the last dose date of a given period of time. Specifically, the duration (days) is calculated as (LASTDAY - FIRSTDAY + 1 day), where LASTDAY is the date of last dose, and FIRSTDAY is the date of first dose.

The date of the first dose is captured by the eCRF question, “Date of first dose?” The first dose date at the 100 mg tildacerfont QD and 200 mg tildacerfont QD is presumed to be the same as the dispensed date at the Week 4 and Week 8 visits, respectively.

The last dose date can be the last dose date of a treatment dose level or treatment end date.

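### The SAP assigns an adverse event to the dose received on its onset date, so an event dated to a Week 4 or Week 8 visit morning is counted at a dose not yet taken; dose-level counts shift upward, and the rule conflicts with SAP 9.3.17.

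*SAP*

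**What the plan says.** **Rule for adverse events.** SAP 9.3.17.1 gives the dose level of a treatment-emergent event by calendar date: it "will be the actual tildacerfont dose received on the onset date of the TEAE records".

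**Start of each new dose.** SAP 9.3.14.3 states that the first dose date at 100 mg and at 200 mg "is presumed to be the same as the dispensed date at the Week 4 and Week 8 visits, respectively".

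**Time of day.** Protocol 3.1.2: "Clinic visits should be scheduled for early in the morning to accommodate morning laboratory assessments". Protocol 7.1.5: "Samples for clinical laboratories will be collected consistently at the beginning of each visit at approximately 8 A.M". Protocol 5.1: "Study drug will be taken with the subject's evening meal". The footnote on the meal in Protocol 12.2 adds "which should be eaten between 6 P.M. and midnight". Protocol 5.5 has the previous supply handed back at the visit: "Study drug will be returned for accountability at Week 4, Week 8, and Week 12".

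**Rules that point the other way.** In the planned-treatment table of SAP 9.3.17, 50 mg runs through Week 4 and 100 mg begins after it, with the same pattern at Week 8. For actual treatment, the same section uses the study drug and "dose level a subject was on when a data record was measured/assessed". SAP 14.2 summarises laboratory results by the treatment actually received at each scheduled time point.

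**Tie-break.** SAP 9.3.16 and Protocol 7.2.1 use onset time, before or after intake, for the date of the very first dose only. Protocol 7.2.3 otherwise lists start and end dates for an adverse event, not times.

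**The concern.** On the two escalation dates, the only dose presumed to be received is the new one, and it is taken hours after the morning assessments. A finding made that morning arose under the earlier dose, but the onset-date rule counts it under the later one. The plan deals with this problem on Day 1 and leaves it open at Weeks 4 and 8.

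Two things follow. First, the tables can disagree: a Week 4 ALT result can be a 50 mg value in the laboratory summary while the adverse event raised from it is a 100 mg event. Second, the error runs in one direction. The 50 mg level loses events, the 100 mg level exchanges its own for those of 50 mg, and the 200 mg level gains events while keeping its own from Week 12. Protocol 1.3 names liver toxicity and QT prolongation among the potential risks, and the Schedule of Activities plans on-treatment laboratory tests and ECGs after Day 1 only at Weeks 4, 8 and 12. Two of those three visits are escalation dates.

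**Working it through.** The documents give no figure that depends on this rule, so there is none to reproduce. The check sets out the timing and then calculates expected counts under no dose effect.

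**Timing on an escalation date**
- About 8 A.M.: samples drawn. The last dose taken is the earlier level, the evening before.
- At the visit: earlier supply returned, new supply dispensed.
- 6 P.M. to midnight: first dose at the new level, 10 to 16 hours after a nominal 8 A.M. draw.
- Dose received on that calendar date: the new level only.

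**(a) Events with onset dated to a visit day**

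Inputs: n = 26 tildacerfont subjects (Protocol 8.1) and an assumed probability p of such an event at each of Weeks 4, 8 and 12, independent between visits. The documents do not define the onset date of a laboratory event; taking it as the sampling date is also an assumption.

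- By last dose taken before onset: np, np, np at 50/100/200 mg.
- By the onset-date rule: Week 4 events go to 100 mg, Week 8 events to 200 mg, and Week 12 events stay at 200 mg. This gives 0, np, 2np.

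| p (assumed) | Expected counts, last dose before onset | Expected counts, onset-date rule | Chance of strictly rising counts: last dose before onset | Chance of strictly rising counts: onset-date rule |
|---|---|---|---|---|
| 5% | 1.3 / 1.3 / 1.3 | 0 / 1.3 / 2.6 | 6% | 41% |
| 10% | 2.6 / 2.6 / 2.6 | 0 / 2.6 / 5.2 | 9% | 70% |
| 20% | 5.2 / 5.2 / 5.2 | 0 / 5.2 / 10.4 | 10% | 87% |

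The chances come from 200,000 simulated trials, counting each subject once per dose level as SAP 14.1 does. The 0:1:2 split of events does not depend on n.

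**(b) All treatment-emergent events**

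Let a share s have visit-day onset, spread equally over the three visits. The rest start uniformly over three 28-day periods, with at most 1 day in 28 moved at each escalation.

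- 50 mg share: (1 − s)/3 × 27/28
- 100 mg share: 1/3 (it gains as much as it loses)
- 200 mg share: 2s/3 + (1 − s)/3 × 29/28

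For s = 10%: 50 mg = 0.300 × 27/28 = 0.2893; 200 mg = 0.0667 + 0.300 × 29/28 = 0.3774; ratio = 0.3774/0.2893 = 1.30.

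| s (assumed) | 50 mg | 100 mg | 200 mg | 200:50 ratio |
|---|---|---|---|---|
| 0% | 0.3214 | 0.3333 | 0.3452 | 1.07 |
| 5% | 0.3054 | 0.3333 | 0.3613 | 1.18 |
| 10% | 0.2893 | 0.3333 | 0.3774 | 1.30 |
| 25% | 0.2411 | 0.3333 | 0.4256 | 1.77 |
| 50% | 0.1607 | 0.3333 | 0.5060 | 3.15 |

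The true ratio in every row is 1.00.

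**The case against.** **The literal reading may not be the intended one.** Section 9.3.17.1 sits under 9.3.17, whose actual-dose sentence covers any data record and would keep a Week 4 morning event at 50 mg. The presumed start date is in the exposure-duration section, and the SAP does not say that it governs event attribution. This stands as evidence of a conflict, but it does not settle it. Section 9.3.17.1 is the specific rule for adverse events, and a programmer would normally apply the specific rule.

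**Few events may be affected.** Attribution follows onset, not detection. A symptom reported at Week 4 that began earlier stays at 50 mg. The C-SSRS after screening asks about the interval since the last visit (Protocol 7.1.6.1). A low cortisol value without other findings is not an adverse event until a repeat confirms it (Protocol 6.1.6). Other abnormal results become adverse events only under the conditions in Protocol 7.2.1. All of this stands, and it limits the size of the shift.

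**Little rests on the dose-level counts.** The tables by system organ class and preferred term are worded by treatment group (SAP 14.1), as is Protocol 8.3.5. Display by dose level rests on the general wording of SAP 14 and the protocol synopsis. Every tildacerfont subject escalates in the same order, so dose is confounded with time and cumulative exposure even with perfect attribution. SAP 15 reports early discontinuation, so absolute counts would be below those for n = 26. These points stand. They confine the consequence to descriptive summaries but do not make the attribution correct.

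**A stronger reading is tempting.** A reader might infer that every event found at these visits moves, that most laboratory, ECG and C-SSRS events are dated there, and that the study would therefore report a false dose-toxicity trend. The documents do not support this. Only events with onset dated to the visit day move, and no passage gives the share of events that would be.

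**Conclusion.** The point holds as a one-directional misattribution written into the SAP and in conflict with a neighbouring section. For events with onset on a visit day the distortion is complete: 0:1:2 instead of 1:1:1. For the full set of treatment-emergent events it is modest if few are visit-detected, about 7% to 30% excess at 200 mg relative to 50 mg for shares of 0% to 10%, and larger as that share grows. A severalfold distortion would need about half of all events to have visit-day onset, and the documents give no sign of that.

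These sizes rest on the assumed values of p and s, on equal event rates across periods, and on the sampling date being recorded as onset. The direction of the shift does not depend on p or s. Tildacerfont overall versus placebo is unaffected. The study stopping criteria in Protocol 6.1.9 do not use dose-level counts. The plan should be corrected because dose-level safety summaries are planned and the rule is stated explicitly, but the matter is one of descriptive reporting, not of the trial's main comparison.

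**What to change.** Reword SAP 9.3.17.1 so that a treatment-emergent event is assigned to the last dose level taken before its onset. Add that an event with onset on a Week 4 or Week 8 dispensing date defaults to the pre-escalation dose level, unless a recorded onset time places it after the first dose at the new level. This brings the section into line with SAP 9.3.17 and 14.2 and extends to the escalation dates the principle that SAP 9.3.16 applies to the first-dose date. Because adverse event timing is otherwise collected as dates, the default will decide most cases and must be stated. The change should be made before unblinding.

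The cost is one sentence or two in the SAP and a small change to the derivation in the analysis dataset. The downside is small: an event that truly starts late on the escalation evening, with no recorded time, is counted at the lower dose. With a half-life of about 60 hours and about 2 weeks to steady state (Protocol 1.2.2 and 1.2.1), exposure in those few hours would still come largely from the earlier dose level.

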8.3.5. Safety Analyses

Safety analyses will be conducted on the Safety Population. All safety data will be listed by subject. Summary tables will be provided for AEs, hematology and chemistry laboratory results, vital signs, and ECG findings. Safety data will be summarized by treatment group using frequency of event or descriptive statistics, as appropriate. Physical examinations will be presented in listings only with abnormal findings documented as AEs.

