5 STUDY DESIGN

This is a multi-center, randomized, placebo-controlled, dose escalation clinical study that will evaluate the preliminary safety and efficacy of up to 12 weeks of double-blinded treatment with tildacerfont (50 mg, 100 mg, and 200 mg once daily [QD]) in adult women subjects with PCOS who have elevated adrenal androgens at baseline. Up to approximately 40 adult subjects will be randomized into the study.

Subjects who meet all eligibility criteria at Screening will be randomized into the Treatment Period in a 2:1 ratio to receive either tildacerfont or matching placebo. Subjects randomized to the tildacerfont group will receive 3 escalating dose levels of tildacerfont with each dose level administered for 4 weeks. Subjects randomized to placebo will remain on placebo over the full 12-week Treatment Period. Upon completion of the Treatment Period, subjects will return to the clinic within 30 days following their last dose for a Follow-up visit.

Clinical visits during the Treatment Period and Follow-up Period will include safety, efficacy, and PK assessments. [Figure 1](#) depicts study visits from Screening Period to Follow-up Period.

The maximum duration of Study SPR001-210 per subject is expected to be up to 204 days (i.e., up to 30 days of optional DHEAS screening, a maximum of 30-day Screening Period, a 12-week Treatment Period, and a 30-day safety Follow-up Period). Subjects randomized to tildacerfont will receive up to 12 weeks of treatment with tildacerfont. Assessments and procedures for evaluation of safety, efficacy, and PK will be conducted per the protocol-specified schedule (see Appendix A: [Table 6](#) and [Table 7](#)).

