5.2.3.2 Physical Examinations

A full physical examination should include assessments of the cardiovascular, respiratory, GI, neurological, and musculoskeletal systems; head, eyes, ears, neck, and throat (HEENT); thyroid; skin; and extremities. The full physical examination may exclude rectal, genitourinary, and breast exams.

An abbreviated physical examination includes the following components: cardiovascular, respiratory, abdomen, musculoskeletal, HEENT, and skin.

A full physical examination will be performed during the Day 1 and Week 12 visits. Abbreviated physical examinations will be performed at Week 4 and Week 8.

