14 SAFETY ANALYSES

Safety will be assessed by AEs, SAEs, AEs leading to discontinuation/withdrawal, DLTs, AESIs, physical examination, vital signs, ECGs, clinical laboratory tests, and psychiatric evaluations for suicide risk by C-SSRS. All analyses of the safety data will be performed using

the safety analysis set, based on the actual treatment a subject received. All descriptive statistics (described in Section 9.1) will be presented by treatment group (including dose level).

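### Assigning the 30-day post-treatment tail to the last dose gives 200 mg about twice the adverse-event window of 50 or 100 mg, so crude percentages by dose level can show a spurious step at 200 mg

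*SAP*

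**What the plan says.** SAP 5 states that subjects on tildacerfont "will receive 3 escalating dose levels of tildacerfont with each dose level administered for 4 weeks"; the order is fixed at 50, 100, then 200 mg. Under SAP 9.3.17.1 the dose level attached to a treatment-emergent event "will be the actual tildacerfont dose received on the onset date of the TEAE records", and an event in the 30 days after study drug discontinuation "will be assigned the last treatment and dose level that the subject was on before study drug discontinuation". Protocol 7.2.1 and SAP 9.3.16 both carry the treatment-emergent period to 30 days after the final dose.

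SAP 14 says that the safety descriptive statistics "will be presented by treatment group (including dose level"). The Protocol synopsis likewise has safety data summarised by group and dose. SAP 14.1 counts subjects rather than events and reports numbers and percentages. SAP 9.1 bases adverse-event percentages on the subjects who received study drug, not on person-time. Neither SAP 14 nor SAP 14.1 plans an exposure-adjusted rate, a restriction to time on each dose, or a separate post-treatment column.

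**The concern.** A crude percentage of subjects with at least one event grows with the length of observation. The attribution rule adds the off-drug follow-up of every completer to one level only, the highest. A reader who compares the three dose columns would then see more subjects with events at 200 mg even if the drug had no dose-related toxicity, and could take this for a tolerability signal at the top dose. Because the study was set up to examine a range of doses, that misreading could affect which doses are taken forward.

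**Working it through.** The documents give no figure for adverse-event observation time by dose level, so there is no stated number to reproduce. The windows follow from the rules.

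**Inputs**
- Time at each level: 4 weeks = 28 days (SAP 5).
- Tail: up to 30 days, assigned to the last level (SAP 9.3.17.1). The follow-up contact falls within 30 days of the last dose (Protocol 3.1.2.5), so 30 is a maximum.
- Half-life: about 60 hours (Protocol 1.2.2). Five half-lives = 5 × 60 / 24 = 12.5 days.
- Planned tildacerfont group 26, dropout 15% (Protocol 8.1).
- Assumption: the documents give no event rate, so the 28-day incidence p is varied from 10% to 40%, with the same constant hazard at every dose.

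**Windows for a completer**
- 50 mg: 28 days. 100 mg: 28 days. 200 mg: 28 + 30 = 58 days.
- Ratio 58 / 28 = 2.07. Share of the total at 200 mg: 58 / (28 + 28 + 58) = 58 / 114 = 51%.

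**Displayed incidence at 200 mg, full tail:** 1 − (1 − p)^(58/28)

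| p at 50 and 100 mg | shown at 200 mg | ratio |
|---|---|---|
| 10% | 19.6% | 1.96 |
| 20% | 37.0% | 1.85 |
| 30% | 52.2% | 1.74 |
| 40% | 65.3% | 1.63 |

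**Shorter effective tail, p = 20%**
- Events only in the first 15 days: 1 − 0.8^(43/28) = 29.0%.
- Events only in the first 12.5 days: 1 − 0.8^(40.5/28) = 27.6%.

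**Early discontinuers.** Their tail goes to 50 or 100 mg. With 15% loss at a constant hazard over 84 days, h = −ln(0.85)/84 per day. The numbers entering the three levels are 26, 24.6 and 23.3, and about 1.2 to 1.4 subjects stop within each level. On-dose time averages 27.3 days per subject entering a level. At 50 and 100 mg the tail adds 30 × (1 − e^(−28h)) = 1.6 days per subject entering, and at 200 mg it adds 30 days. The average windows are 28.8, 28.8 and 57.3 days. At p = 20% the displayed incidence is 20.5%, 20.5% and 36.6% of those entering each level. With all 26 as the denominator it is 20.5%, 19.4% and 32.8%. The step remains on either denominator.

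**After the change.** With on-dose days only, the windows for a completer are 28, 28 and 28 days, and equal hazards show as 20%, 20% and 20%. Equivalently, the rate is −ln(0.8)/28 = 0.0080 per person-day at every level.

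**The case against.** Several points on the other side have force.

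- **The attribution rule is reasonable in itself.** With a half-life near 60 hours, drug remains after the last 200 mg dose, and linking early post-dose events to that dose is sensible. This supports labelling the tail by last dose. It does not support merging the tail into a column compared with two columns that have none.
- **The tail may yield few events.** It has one review, which may be by telephone (Protocol 3.1.2.5), against a telephone call and a clinic visit in each treatment period. Events that cluster at first exposure would pull the other way. This stands, which is why the size is given as a range.
- **The rule may not cover completers.** It speaks of "Post-treatment AEs (within 30 days after study drug discontinuation) will be assigned the last treatment and dose level", and Protocol 6.1 and SAP 9.3.16 use discontinuation for stopping early, while SAP 9.3.3 defines completion separately. On that narrow reading, completers' post-treatment events have no stated dose, which is a different gap. The proposed wording closes it too.
- **The consequence is limited.** No dose-trend test on adverse events is planned. SAP 14.1 describes the system organ class and preferred term tables by treatment group only; dose level comes from the general sentence in SAP 14 and from the synopsis. All events are listed, and SAP 15 records that the study stopped early with a small sample. If by-dose event tables are not intended, the SAP should say so.
- **Equal windows do not make the doses comparable.** Escalation is in fixed order, so dose stays confounded with time on study.

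A reader might also infer that observation is more intensive at 200 mg because of the physical examinations. SAP 5.2.3.2 says "A full physical examination will be performed during the Day 1 and Week 12 visits", the Day 1 examination is before dosing, footnote 9 to Protocol 12.2 says "Abbreviated physical examinations at Visits 2 and 3 will be conducted directed by" adverse events, and Protocol 8.3.5 says "Physical examinations will be presented in listings only with abnormal findings documented as AEs". The documents do not carry that inference far. Vital signs, ECG, C-SSRS and safety bloods are the same at Weeks 4, 8 and 12. The abbreviated examination already covers most body systems. A Week 12 finding goes to 200 mg only if its onset is dated within that period. The size of any effect cannot be derived.

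**Conclusion.** The point holds as a spurious step at 200 mg. If SAP 9.3.17.1 covers completers, the 200 mg window is up to 58 days against 28 and 28, and the planned crude percentages do not correct for it. At an assumed 20% per 28 days with equal hazards, 50, 100 and 200 mg would show about 20%, 20% and 28% to 37%. With a full tail and constant hazard, the ratio of 200 mg to either lower dose is 1.96 to 1.63 for incidences of 10% to 40%. The direction follows from the rule as long as the tail yields events; the size rests on assumed rates.

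A reader might go further and conclude that incidence rises with dose by construction. The documents do not support that: 50 and 100 mg have equal windows and the same scheduled assessments, and early discontinuers add only about 1.6 days per subject to each. The overall comparison of tildacerfont with placebo is unaffected, because both arms have the same 84 + 30 days.

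**What to change.** In SAP 9.3.17.1 and 14.1:

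1. Base the by-dose summaries of treatment-emergent events on on-treatment days at each level, or give exposure-adjusted rates. If rates are used, numerator and denominator must cover the same days: exposure duration in SAP 9.3.14.3 ends at the last dose, so tail events must not be divided by it.
2. Show events in the 30 days after the last dose in a separate post-treatment column labelled by last dose, and state that this applies to completers as well as to early discontinuers.
3. State which level the Week 4 and Week 8 visit days belong to. SAP 9.3.14.3 presumes that the new level starts on those days, while SAP 9.3.17 starts it after Week 4 and after Week 8.
4. Keep the full-window tildacerfont versus placebo table as the main safety comparison.

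At most, add a note beside the by-dose tables that Week 12 has the only scheduled full physical examination on treatment. A flag for events first found at that examination is not proposed, because method of detection is not among the adverse-event data listed in Protocol 7.2.3.

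The cost is SAP wording and one extra column. The downside is that early post-dose events under residual 200 mg exposure appear in the post-treatment column instead of the 200 mg column. No event is lost. The confounding of dose with time on study remains and should be stated as a limitation.
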